### **8.2.1.1. Relationship to Study Drug**

The Investigator must assess whether the AE may be related to each study drug or trial-mandated procedure, when applicable. The relationship is defined below:

*Relationship assessments that indicate the event is “not drug related”:*

- None: The event is related to an etiology other than the study drug administration (the alternative etiology must be documented in the trial patient’s medical record).
- Remote: The event is unlikely to be related to the study drug and likely to be related to factors other than study product.

*Relationship assessments that indicate the event is “drug related”:*

- Possible: There is an association between the event and the administration of study drug, and there is a plausible mechanism for the event to be related to the study drug; but there may also be alternative etiology, such as characteristics of the patient’s clinical status or underlying disease.
- Probable: There is an association between the event and the administration of study drug, there is a plausible mechanism for the event to be related to the study drug, and the event could not be reasonably explained by known characteristics of the patient’s clinical status or an alternative etiology is not apparent.
- Definite: There is an association between the event and the administration of study drug, there is a plausible mechanism for the event to be related to the study drug, and causes other than study drug have been ruled out and/or the event reappeared on re-exposure to study drug.

### **8.2.1.2. Adverse Event Severity**

The Investigator will assess the grade of the AE per the NCI-CTCAE version 5.0 or higher. Toxicities that are not specified in NCI-CTCAE will be defined as follows:

- Grade 1: mild; asymptomatic or mild symptoms; clinical or diagnostic observations only; intervention not indicated
- Grade 2: moderate; minimal, local, or noninvasive intervention indicated; limiting age-appropriate instrumental activities of daily living (ADL)
- Grade 3: severe or medically significant but not immediately life-threatening; hospitalization or prolongation of hospitalization indicated; disabling; limiting self-care ADL
- Grade 4: life-threatening consequences; urgent intervention indicated

- Grade 5: death related to AE

Note: It is important to distinguish between SAEs and severe AEs. Severity is a measure of intensity, whereas seriousness is classified by the criteria based on the regulatory definitions as described in Section 8.1.2 above.

#### **8.2.1.3. Abnormal Laboratory and Electrocardiogram Values**

The Investigator is responsible for reviewing clinical laboratory test and ECG results and determining whether an abnormal value in a patient represents a clinically significant change from the patient's Baseline value. In general, abnormal laboratory findings and ECGs without clinical significance (based on the Investigator's judgment) should not be recorded as AEs. In general, an abnormal laboratory test and ECG results should be reported as an AE if the laboratory result:

- Requires an adjustment or discontinuation of study drug
- Requires treatment or adjustment to concomitant medications
- Is considered to be an AE by the Investigator

#### **8.2.1.4. Medication Errors, Misuse, and Abuse of Study Drug**

Overdose, medication error, misuse, and abuse are defined as follows:

- Medication error: refers to an unintentional error in dispensing or administration of study drug not in accordance with the protocol
- Off-label use: relates to situations where the study drug is intentionally used for medical purpose not in accordance with the protocol
- Misuse: refers to situations where the study drug is intentionally and inappropriately used not in accordance with the protocol
- Abuse: corresponds to the persistent or sporadic, intentional excessive use of the study drug, which is accompanied by harmful physical or psychological effects
- Occupational exposure: refers to the exposure to the study drug because of one's professional or nonprofessional occupation

No specific information is available on the treatment of overdose of study drug. In the event of overdose, the patient should be observed closely for signs of toxicity. Appropriate supportive treatment should be provided if clinically indicated.

Overdoses, medication errors, abuse, and misuse will be collected as part of investigational medicinal product dosing information and/or as protocol violations, as required.

#### **8.2.2. Reporting of Serious Adverse Events and Adverse Events of Special Interest**

An SAE/AESI report form will be completed in the electronic data capture (EDC) system and submitted to the Sponsor or designee within 24 hours of the Investigator's first knowledge of the event, even if the experience does not appear to be related to study drug, from the time of signing the ICF through 30 days after the last dose of SRF617, 30 days after the last dose of etrumadenant, or 90 days after the last dose of zimberelimab (30 days after the last dose of

zimberelimab if the patient initiates new anticancer therapy), whichever is later. In the event that EDC is unavailable, the SAE/AESI paper report form must be filled out by the Investigator and sent via email within 24 hours of awareness of the event to the Clinipace Pharmacovigilance Department ([contact]), and then the information entered into the EDC once available.

**Please refer to the SAE/AESI report form and completion guidelines for more detailed instructions.**

The initial SAE/AESI report must be as complete as possible, including details of the current illness and SAE/AESI and an assessment of the relationship between the event and study drugs. Additional information relating to a previously reported SAE/AESI must also be reported within 24 hours of the Investigator's first knowledge of information. The Investigator may also be asked, by the Sponsor, to provide clarifications or additional information.

If the Investigator becomes aware of an SAE/AESI considered related to study drug(s) by the Investigator occurring more than 30 days after the last dose of SRF617, 30 days after the last dose of etrumadenant, or 90 days after the last dose of zimberelimab, the SAE must be reported as described above.

#### **8.2.2.1. Reporting of Serious Adverse Events to Regulatory Authorities, Ethics Committee, and Institutional Review Board**

The Sponsor or designee will determine expectedness for each reported SAE based on the appropriate reference safety information for the study drug per local requirements. The Sponsor or designee shall notify regulatory authorities of serious, unexpected, and related AEs or other AEs, per local requirements.

The Sponsor or designee shall notify the Investigator of serious, related, and unexpected AE(s) submitted to the regulatory agencies, per local country requirements.

The Investigator shall notify the Central Ethics Committees of serious, related, and unexpected AE(s), or significant risks to patients, per country requirements.

The Investigator will notify the appropriate IRB/Local Ethics Committees of serious, related, and unexpected AE(s), or significant risks to patients, per local country requirements. The Investigator must keep copies of all AE information on file, including correspondence with the Sponsor or IRBs/IECs.

#### **8.2.2.2. Reporting Adverse Events of Special Interest**

AESIs for this trial are defined as thromboembolic events, eg, DVT, pulmonary embolism, stroke, myocardial infarction. The Investigator should report both serious and nonserious thromboembolic events to the Sponsor using the same methods as described for reporting SAEs.

#### **8.2.3. Pregnancy and In Utero Drug Exposure**

Pregnancies occurring in partners of male patients are considered immediately reportable events if the pregnancy occurs during the study treatment period through 30 days after the patient's last dose of SRF617, 30 days after the last dose of etrumadenant, or 90 days after the last dose of

zimberelimab, whichever is later. The Investigator will attempt to collect pregnancy information on any male patient's female partner who becomes pregnant while the male patient is in this trial.

Please refer to the pregnancy notification form or pregnancy outcome form and associated completion guidelines on where and how to submit the forms.

## **9. STATISTICAL METHODS**

Details of the statistical methods for this trial will be documented in a statistical analysis plan (SAP). The SAP may modify the statistical methods outlined in the protocol; however, any major modification will also be reflected in a protocol amendment.

### **9.1. Sample Size**

This trial will enroll approximately 40 patients. A patient is enrolled in the trial after they have provided informed consent and met all trial eligibility criteria.

A Simon 2-stage design will be implemented. Simon Stage 1 will include a 6-patient Safety Lead-in followed by enrollment of an additional 11 patients for a total of 17 patients. At least 1 radiographic CR/PR or 2 PSA50 responses by PCWG3 criteria out of 17 evaluable patients must be observed in order to consider opening Stage 2, which will enroll an additional 23 patients for further evaluation of the safety and efficacy of the triplet. The trial will have met its primary endpoint if at least 8 patients in total achieve a response.

The sample size for this triplet combination therapy dose expansion is based on a null hypothesis of a 10% composite response rate (PSA50 or CR/PR) with PD-1 blockade alone versus the alternate hypothesis that the composite response rate is 30%, with a calculated alpha of 0.040 and power of 0.93.

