### **Trial Design:**

This Phase 2, open-label, safety and preliminary efficacy trial in patients with mCRPC will employ a Simon 2-stage design with an integrated safety lead-in for the triplet combination of SRF617, etrumadenant, and zimberelimab. Cycles are 28 days in duration. Stage 1 will enroll approximately 17 patients, including the Safety Lead-in that will initially treat 6 patients. After the first 6 patients have been enrolled, enrollment will be paused until these patients have received 1 cycle of the triplet combination and the Safety Review Committee (SRC) has reviewed the aggregate safety data. Once the SRC deems it safe to proceed, an additional 11 patients will be enrolled. Based on an evaluation of safety and response data, the trial will proceed to the Stage 2 expansion if  $\geq 1$  radiographic complete response (CR)/partial response (PR) or 2 prostate-specific antigen (PSA) responses (defined as a  $\geq 50\%$  decline [PSA50]) according to the Prostate Cancer Working Group 3 (PCWG3) criteria are observed in 17 evaluable patients. An additional 23 patients will be enrolled in Stage 2 for further evaluation of the safety and efficacy of the combination. Tumor biopsies are optional; they will be performed to explore potential biomarkers of response to the combination in patients who consent to the procedure, who have non-bone metastases amenable to biopsy, and for whom the procedure is deemed safe.

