**Statistical Methodology**

**Sample Size Determination**

This trial will enroll approximately 40 patients. A patient is enrolled in the trial after they have provided informed consent and met all trial eligibility criteria.

A Simon 2-stage design will be implemented. Simon Stage 1 will include a 6-patient Safety Lead-in followed by enrollment of an additional 11 patients for a total of 17 patients. At least 1 radiographic CR/PR or 2 PSA50 responses by PCWG3 criteria out of 17 evaluable patients must be observed in order to consider opening Stage 2, which will enroll an additional 23 patients for further evaluation of the safety and efficacy of the triplet. The trial will have met its primary endpoint if at least 8 patients in total achieve a response.

The sample size for this triplet combination therapy dose expansion is based on a null hypothesis of a 10% composite response rate (PSA50 or CR/PR) with PD-1 blockade alone versus the alternate hypothesis that the composite response rate is 30%, with a calculated alpha of 0.040 and power of 0.93.

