### **4.2. Stage 2**

Based on an evaluation of safety and response data, the trial will proceed to the Stage 2 expansion if  $\geq 1$  radiographic CR/PR or 2 PSA responses (defined as a  $\geq 50\%$  decline [PSA50]) according to PCWG3 criteria are observed in 17 evaluable patients. An additional 23 patients will be enrolled in Stage 2 for further evaluation of the safety and efficacy of the combination.

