### **4.3. Safety Review Committee**

This trial will use an SRC, which will meet regularly throughout the trial to review all available safety, PK, and preliminary efficacy data. The SRC will be composed of a medical representative from the Sponsor, a Medical/Safety Monitor from the Contract Research Organization supporting the trial (if applicable), and all Principal Investigators (or their specified delegates) at each of the enrolling sites. The SRC may recommend investigating intermediate doses or alternative schedules for administration of SRF617 to optimize combination dose determination. The SRC may recommend halting or stopping the trial at any time based on a comprehensive review of all clinical data.

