## 5. TRIAL POPULATION

### 5.1. Inclusion Criteria

All patients must meet the following criteria for inclusion:

1. Males  $\geq$  18 years of age on the day of signing informed consent.
2. Metastatic castration-resistant prostate cancer with castrate levels of testosterone ( $\leq$  50 ng/dL or  $\leq$  1.7 nmol/L).
3. Eastern Cooperative Oncology Group (ECOG) performance status of 0 to 1.
4. Must have progressed (by PSA or radiologic criteria) during or following treatment with a novel ARSI (eg, abiraterone, enzalutamide, apalutamide, darolutamide), which may have been given for either hormone-sensitive prostate cancer (HSPC) or CRPC.
5. Must have received 1 to 2 prior lines of taxane chemotherapy, unless the physician and patient believe the patient is medically ineligible or the patient refuses (ineligibility or refusal must be documented in the source documents).
6. Must have progressed by PSA or radiologic criteria on or during last therapy for prostate cancer.
7. Measurable or non-measurable disease as per radiographic evaluation. Lesions situated in a previously irradiated area are considered evaluable if progression has been demonstrated in such lesions since radiation.
  - Note: If disease is considered non-measurable, a minimum PSA of 1 ng/dL is required with at least 1 confirmed rise at a minimum of a 1-week interval.
8. Washout period from the last dose of previous anticancer therapy (chemotherapy, biologic, or other investigational agent) to the first dose of study drug must be  $>$  5 times the half-life of the agent or  $>$  21 days, whichever is shorter. The washout period for palliative radiation (defined as  $\leq$  2 weeks of radiation) to non-central nervous system (CNS) disease is  $>$  7 days.
9. Resolution of non-immune-related AEs secondary to prior anticancer therapy (excluding alopecia and peripheral neuropathy) to Grade  $\leq$  1 per NCI-CTCAE version 5.0 or higher, and complete resolution of immune-related AEs secondary to prior immunotherapy.
  - Note: Patients with the following clinically stable or clinically nonsignificant immune-related AEs are permitted: Controlled thyroid disorders, vitiligo, asymptomatic elevated amylase/lipase, type 1 diabetes on insulin, Grade  $\leq$  2 controlled rash, Grade  $\leq$  2 electrolyte abnormalities on stable dose of supplementation.

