2.3 Sample Size Considerations

This trial will enroll approximately 40 patients. A patient is enrolled in the trial after they have provided informed consent and met all trial eligibility criteria.

A 2-stage design will be implemented. Stage 1 will include a 6-patient Safety Lead-in followed by enrollment of an additional 11 patients for a total of 17 patients. At least 1 radiographic CR/PR or 2 PSA₅₀ responses by PCWG3 criteria out of 17 evaluable patients must be observed in order to consider opening Stage 2, which will enroll an additional 23 patients for further evaluation of the safety and efficacy of the triplet. The trial will have met its primary endpoint if at least 8 patients in total achieve a response.

The sample size for this triplet combination therapy dose expansion is based on a null hypothesis of a 10% composite response rate (PSA₅₀ or CR/PR) with PD-1 blockade alone versus the alternate hypothesis that the composite response rate is 30%, with a calculated alpha of 0.040 and power of 0.93.

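### Do the stated alpha of 0.040 and power of 0.93 belong to a different Stage 1 rule from the one written down, and does that matter?

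*Protocol*

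**What the plan says.** Protocol 9.1 sets the Stage 1 threshold as "At least 1 radiographic CR/PR or 2 PSA 50 responses by PCWG3 criteria out of 17 evaluable patients", and the synopsis adds that this "must be observed in order to consider opening Stage 2". SAP 2.3 repeats it: "At least 1 radiographic CR/PR or 2 PSA₅₀ responses by PCWG3 criteria out of 17 evaluable patients". The synopsis paragraph on trial design also carries the numeral, "or 2 prostate-specific antigen (PSA) responses". Success at the end is 8 or more responders among 40. The sample size is justified by a composite rate of 10% under the null and 30% under the alternative, "with a calculated alpha of 0.040 and power of 0.93". Neither document gives a probability of stopping after Stage 1, or the expected share of responses that are radiographic.

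The force of the threshold varies a little. Protocol 9.1 and SAP 2.3 make it a condition for considering Stage 2, while Protocol 4.2 says "the trial will proceed to the Stage 2 expansion if" the threshold is met, on an evaluation of safety as well as response. Protocol 4.3 adds that "The SRC may recommend halting or stopping the trial at any time based on a comprehensive review of all clinical data".

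SAP Section 2 restates the Stage 1 rule with no number in front of the PSA responses. SAP 1.1 lists no change to the rule. It records that the sponsor ended the study with 15 patients treated, and SAP 13 makes the Stage 1 analysis the final one.

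**The concern.** Two things look wrong.

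First, a reader who checks the design finds that 0.040 and 0.93 match a plain Simon rule counting composite responders, with a cutoff of 2 of 17. The written rule treats the two kinds of response differently: one radiographic response is enough, but two PSA responses are needed if there is no radiographic one. The quoted operating characteristics therefore seem to belong to another design. A two-stage design exists to stop early when the treatment is inactive, and someone reconstructing it from the stated pair would credit it with a 48.2% chance of stopping that the written rule does not guarantee.

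Second, SAP Section 2 read literally lets a single PSA response open Stage 2, which fails under SAP 2.3 and the protocol. The SAP then holds two thresholds for the only efficacy gate in the trial.

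**Working it through.** **Inputs** (Protocol 9.1, SAP 2.3): n1 = 17, n2 = 23, success at ≥ 8 of 40, p0 = 0.10, p1 = 0.30. One input is not in the documents and is assumed over its whole range: s, the probability that a sole Stage 1 responder has a radiographic CR/PR, from 0 to 1. Protocol 5.1 admits "Measurable or non-measurable disease as per radiographic evaluation", so s = 1 is unlikely, but nothing fixes it.

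**Reproducing the stated pair.** P(success) = Σ P(X1 = x) · P(X2 ≥ 8 − x), summed over the Stage 1 counts x that pass.

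| Passes Stage 1 at | Alpha | Power |
|---|---|---|
| ≥ 1 of 17 | 0.0417 | 0.944 |
| **≥ 2 of 17** | **0.0399** | **0.934** |
| ≥ 3 of 17 | 0.0335 | 0.892 |
| no interim look, 40 patients | 0.0419 | 0.945 |

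Of these, only ≥ 2 gives both stated figures.

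**Where the written rule differs.** With two or more composite responders, either at least one is radiographic or at least two are PSA responders, so both rules pass. With none, both stop. They part only when there is exactly one responder and that response is radiographic.

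- P(X1 = 0) = 0.9^17 = 0.1668 and P(X1 = 1) = 17 × 0.1 × 0.9^16 = 0.3150 under the null.
- P(X1 = 0) = 0.7^17 = 0.0023 and P(X1 = 1) = 17 × 0.3 × 0.7^16 = 0.01695 under the alternative.
- P(X2 ≥ 7 of 23) = 0.00577 under the null and 0.5601 under the alternative.

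The largest possible shift is therefore 0.3150 × 0.00577 = 0.0018 in alpha and 0.01695 × 0.5601 = 0.0095 in power, both upward.

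Null stopping = 0.1668 + (1 − s) × 0.3150. Expected N = 17 + 23 × (1 − null stopping).

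| s | Alpha | Power | Null stopping | Expected N under null |
|---|---|---|---|---|
| 0 | 0.0399 | 0.934 | 48.2% | 28.9 |
| 0.25 | 0.0403 | 0.937 | 40.3% | 30.7 |
| 0.50 | 0.0408 | 0.939 | 32.4% | 32.5 |
| 0.75 | 0.0412 | 0.941 | 24.6% | 34.4 |
| 1 | 0.0417 | 0.944 | 16.7% | 36.2 |

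Under p = 0.30, stopping runs from 1.9% (s = 0) to 0.2% (s = 1).

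**Distance from the stated figures.** At most 0.0417 − 0.040 = 0.0017 for alpha and 0.9438 − 0.93 = 0.0138 for power, with power understated. Alpha still rounds to 0.040 up to s of about 0.34; power still rounds to 0.93 up to s of about 0.07.

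**A bound that needs no s.** Stopping for futility can only remove successes, so whatever rule opens Stage 2, alpha cannot exceed the single-stage 0.0419 and power cannot exceed 0.945.

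**SAP Section 2 against SAP 2.3.** Read literally, they disagree only when the sole responder is PSA-only: 0.3150 × (1 − s) under the null, at most 31.5%, and at most 1.7% under p = 0.30.

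**The case for a change.** The strongest case for acting is that the loss falls on the feature that justifies two stages. Exactly one responder of 17 is a common null outcome (31.5%), and at s = 0.5 the chance of stopping drops from 48.2% to 32.4%. The study report will take its design description from this SAP, and the remedy would be one numeral and one sentence.

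The calculation stands; the conclusion drawn from it does not. Neither document claims 48.2%, and the written go rule is printed in the same section as alpha and power, so nobody meets the stated pair without the rule beside it. The stopping rates are also floors, because Protocol 9.1 and SAP 2.3 make the threshold necessary but not sufficient and the Safety Review Committee may recommend stopping regardless. Putting a 17–48% range into the SAP would import a radiographic share the trial never specified. Even that range assumes that the CR/PR opening Stage 2 also counts as a composite response. The Stage 1 rule does not ask for confirmation, whereas SAP 10.1.3 does, so null stopping could be lower still.

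The SAP discrepancy is real in the text. But the noun there is plural, the numeral appears in SAP 2.3 and throughout the protocol, and SAP 1.1 records no change. A dropped character is the natural reading, and an analyst would resolve it without instruction.

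**Conclusion.** No change follows. The stated alpha and power are not materially wrong: they are exact for a cutoff of 2 composite responders of 17, and for the written rule they are off by at most about 0.002 and 0.014, with power on the conservative side. False-positive control holds under any Stage 1 rule, since 8 of 40 without an interim look has alpha 0.0419. The looser gate trades some early stopping for a chance to follow up a single radiographic response, a defensible choice in an early efficacy trial. The 16.7–48.2% range for null stopping rests on an undocumented radiographic share and on a Stage 1 CR/PR also being a composite response.

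The missing numeral in SAP Section 2 is a clerical slip. Version 2.0 of the SAP is dated June 2023, after the November 2022 announcement that development would be discontinued. Stage 2 was never opened, and SAP 10.2.1 leaves a proportion with exact intervals and an exact p value against 10%. None of these uses the Stage 1 threshold, so no estimate, interval, p value or decision depends on either point.
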